### 8.3.2 Analysis of Secondary Efficacy Variable

#### 8.3.2.1 Definition of Variable

Dysglycemia categorization: abnormal or normal glucose tolerance as determined by an OGTT, classified as either:

- CFRD: 2-hour post-OGTT blood glucose level  $\geq 200$  mg/dL [ $\geq 11.10$  mmol/L]) or fasting hyperglycemia [blood glucose level  $\geq 126$  mg/dL ( $\geq 7.00$  mmol/L) after an 8-hour fast]
- IGT: 2-hour post-OGTT blood glucose level  $\geq 140$  to  $< 200$  mg/dL [ $\geq 7.77$  to  $< 11.10$  mmol/L] and fasting blood glucose level  $< 126$  mg/dL ( $< 7.00$  mmol/L)
- NGT: 2-hour post-OGTT blood glucose level  $< 140$  mg/dL [ $< 7.77$  mmol/L] and fasting blood glucose level  $< 126$  mg/dL ( $< 7.00$  mmol/L)

Improvement in dysglycemia categorization: response at Week 48 compared to baseline (i.e. CFRD at baseline to IGT or NGT at Week 48, or IGT at baseline to NGT at Week 48 OGTT).

OGTT results are considered valid only when the subject was fasting for at least 8 hours. Any non-fasting OGTT results will be disregarded and data for that assessment will be considered missing.

### **8.3.2.2 Analysis Method**

The number and proportion of subjects with and without response at Week 48, defined as improvement from baseline dysglycemia categorization (i.e. CFRD at baseline to IGT or NGT based on Week 48 OGTT measurement, and IGT at baseline to NGT based on Week 48 OGTT measurement), will be presented for patients with abnormal glucose (CFRD or IGT) at baseline. The exact, 2-sided 95% Clopper-Pearson CI of the proportion of subjects with improvement will also be presented. In addition, the number and proportion of subjects in each dysglycemia category at baseline and each post-baseline visit will be presented.

### **8.3.3 Analysis of Other Variables**

#### **8.3.3.1 Definition of Variables**

Sweat chloride (SwCl): the SwCl value for a given visit will be calculated as the mean of the non-missing sweat chloride measurements obtained on the left and right arms at that visit. If one of the two arm measurements at a time point is missing, the other will be used as the mean. A volume  $\geq 15 \mu\text{L}$  is required for an accurate determination of sweat chloride. Any results reported as having volume  $< 15 \mu\text{L}$  will be considered missing. Any sweat chloride values reported as  $< 10 \text{ mmol/L}$  or  $> 160 \text{ mmol/L}$  will be considered missing.

Body mass index (BMI): the BMI at each visit is calculated using the weight and height at each visit as follows:

$$\text{BMI} = \text{Weight (kg)} / [\text{Height (m)}]^2$$

Continuous glucose monitoring (CGM): CGM will be performed in subjects with CFRD at screening to assess dynamic, free-ranging changes in capillary glucose levels. A CGM sensor will be inserted subcutaneously by site medical staff, a home health nurse, or the subject after adequate training, calibrated, and worn for approximately 7 days. The CGM sensor records glucose values every 5 minutes.

CGM glucose values are considered valid between 39 and 401 mg/dL. Any values reported as  $< 39 \text{ mg/dL}$  or  $> 401 \text{ mg/dL}$  are considered missing. The daily CGM assessment is considered valid when at least 202 values are obtained and valid (at least 70% of 288 5-minute records). For each analysis visit, the CGM parameters will be calculated for each valid daily assessment and then averaged, provided that there are at least 4 valid daily assessments.

#### **8.3.3.2 Analysis Method**

For the following other endpoints, the raw values and change from baseline will be summarized descriptively (n, mean, SD, standard error [SE], median, minimum, and maximum):

- Change from baseline in sweat chloride (SwCl) through Week 48
- Absolute change in body mass index (BMI) from baseline at Week 48
- Absolute change in body weight from baseline at Week 48

- Change from baseline in percent of time spent in target blood glucose range of  $\geq 70$  to  $< 140$  mg/dL ( $\geq 3.89$  to  $< 7.77$  mmol/L) as measured by 7-day CGM in subjects with CFRD at Week 48
- Change from baseline in percent of time spent between  $\geq 140$  and  $< 200$  mg/dL [ $\geq 7.77$  and  $< 11.10$  mmol/L] and percent of time spent  $\geq 200$  mg/dL [ $\geq 11.10$  mmol/L] as measured by 7-day CGM in subjects with CFRD at Week 48

The raw values and change from baseline at each post-baseline visit up to Week 48 will also be summarized descriptively (n, mean, SD, SE, median, minimum, and maximum).

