- Change from baseline in selected CGM parameters (including but not limited to percent of time spent between ≥ 140 and < 200 mg/dL [≥ 7.77 and < 11.10 mmol/L], percent of time spent ≥ 200 mg/dL [≥ 11.10 mmol/L], and maximum amplitude of glucose excursions [MAGE]) in subjects with CFRD at Week 48.

Number of Subjects Approximately 60 subjects will be enrolled, of whom approximately 30 subjects will have IGT and 30 subjects will have CFRD.

Study Population Male and female subjects with CF who are 12 years of age or older, heterozygous for the *F508del* mutation and an MF mutation (F/MF genotypes), with abnormal glucose tolerance as determined by OGTT at screening (classified as either IGT or CFRD). Among all subjects, approximately 50% may be enrolled while using insulin (≤ 0.3 units/kg/day).

Investigational Drug **Active substance:** ELX (VX-445)/TEZ (VX-661)/IVA (VX-770)
Activity: CFTR correctors (ELX and TEZ) and potentiator (IVA)
Strength and route of administration: ELX 100-mg/TEZ 50-mg/IVA 75-mg fixed-dose combination (FDC) tablets, oral

[figure not shown]
Active substance: IVA (VX-770)

Activity: CFTR potentiator

Strength and route of administration: 150-mg tablets, oral

Study Duration Excluding the Screening Period, the total study duration is approximately 52 weeks (48 weeks for the Treatment Period, and 4 weeks for the Safety Follow-up Period).

Study Design This is a Phase 3b, open-label study in CF subjects 12 years of age and older with F/MF genotypes and abnormal glucose tolerance. A schematic of the study design is shown in [Figure 2-1](#).

Figure 2-1 VX19-445-117 Study Design

ELX: elexacaftor; CFRD: CF-related diabetes; CGM: continuous glucose monitoring; IVA: ivacaftor; N: total sample size; TEZ: tezacaftor

- ^a On Day -7, a CGM sensor will be inserted subcutaneously to assess baseline blood glucose levels for 7 days prior to the first dose of study drug in subjects with CFRD.
- ^b Subjects who complete the visits in the Treatment Period, regardless of whether they are on a treatment interruption, will be offered the opportunity to enroll in an open-label extension safety study evaluating ELX/TEZ/IVA. The Safety Follow-up Visit is not required for subjects who complete the Week 48 Visit and have enrolled in an open-label study within 28 days after the last dose of study drug.

Subjects will receive ELX 200 mg once daily (qd)/TEZ 100 mg qd/IVA 150 mg every 12 hours (q12h).

Assessments Efficacy and PD:

- 2-hour OGTT
- SwCl
- BMI

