10.7 Blinding and Unblinding

This is an open-label study; however, subjects and their parent/legal guardian should not be informed of their study-related CGM, SwCl, spirometry, FE-1, and blood biomarker results during the Treatment Period, regardless if the subject permanently discontinues.

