## 6.2 Sample Size and Power

The primary efficacy endpoint is change from baseline in 2-hour blood glucose levels following an OGTT to the average of Week 36 and Week 48. The primary null hypothesis to be tested is that the mean change from baseline in 2-hour blood glucose levels following OGTT to the average of Week 36 and Week 48 is equal to zero.

Assuming a within group standard deviation (SD) of 45 mg/dL and a 10% dropout rate at Week 48, a sample size of 60 subjects will have more than 95% power to detect a mean decrease from baseline of -30 mg/dL in 2-hour blood glucose levels post-OGTT to the average of Week 36 and Week 48, based on a 2-sided, 1-sample t-test at a significance level of 0.05.

All power calculations were based on EAST software Version 6.4.

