#### **8.4.1.1 Adverse Events of Special Interest**

For this study, elevated transaminase events and rash events, as determined by MedDRA preferred terms in [Appendix E](#), are considered as adverse events of special interest.

For treatment-emergent elevated transaminase events and rash events, the following categories will be summarized by treatment group:

- Subjects with events

- Subjects with events by maximum severity
- Subjects with events leading to treatment discontinuation
- Subjects with events leading to treatment interruption
- Subjects with serious events
- Subjects with related serious events
- Subjects with events leading to death
- Duration of events
- Time-to-onset of first event

In addition, for treatment-emergent rash events, these categories will be summarized for the following subgroups:

- Sex (male, female)
- Female subjects with concomitant hormonal therapy (Yes, No)

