#### **8.4.2 Clinical Laboratory**

For the treatment-emergent laboratory measurements, the observed values and change from baseline values of the continuous hematology, serum chemistry, and coagulation results will be summarized in SI units at each visit.

The number and percentage of subjects meeting the threshold analysis criterion at least once during the TE period will be summarized for select LFT parameters. The threshold analysis of shift from baseline will also be summarized for selected LFT laboratory parameters. The threshold analysis criteria are provided in [Appendix F](#).

For selected LFT laboratory tests (alanine transaminase [ALT], aspartate transaminase [AST], alkaline phosphatase [ALP], and total bilirubin), a scatter plot of the maximum treatment-emergent value versus the baseline value corresponding to  $\times$ ULN (upper limit of normal) will be presented. Further, a scatter plot of the maximum treatment-emergent value of ALT and AST, separately, versus the maximum treatment-emergent value of total bilirubin corresponding to  $\times$ ULN will also be presented.

Results of urinalysis and positive urine/serum pregnancy test will be listed in individual subject data listings only. For positive serum pregnancy listing, subjects with serum HCG which are above non-pregnant levels will be selected.

In addition, a listing containing individual subject hematology, chemistry, and coagulation values will be provided. This listing will include data from both scheduled and unscheduled visits.

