**Table 12-3 Threshold Analysis Criteria for Laboratory Tests (as applicable)**

Parameter	Threshold Analysis	Comments
AST and Total Bilirubin	AST>3xULN and TBILI>2xULN	FDA DILI Guidance Jul 2009.
(ALT or AST) and Total Bilirubin	(ALT>3xULN or AST>3xULN) and TBILI>2xULN	FDA DILI Guidance Jul 2009.
GGT	>ULN - ≤ 2.5xULN >2.5 - ≤ 5.0xULN >5.0 - ≤ 20.0xULN >20.0xULN	CTCAE grade 1-4
Clinical Chemistry (NON-LFT)		
Albumin	<LLN - ≥ 30 g/L <30 - ≥ 20 g/L <20 g/L	CTCAE grade 1-3
Amylase	>1x - ≤ 1.5xULN >1.5x - ≤ 2xULN >2x - ≤ 5xULN >5xULN	Criteria based upon CTCAE
Creatinine	>ULN - ≤ 1.5xULN >1.5 - ≤ 3.0xULN >3.0 - ≤ 6.0xULN >6.0xULN	CTCAE grades 1-4
Lipase	>ULN - ≤ 1.5xULN >1.5x - ≤ 2xULN >2x - ≤ 5xULN >5xULN	Criteria based upon CTCAE
Total protein	<LLN >ULN	No CTCAE
Creatine kinase	>ULN - ≤ 2.5 x ULN >2.5 - ≤ 5 x ULN >5 - ≤ 10x ULN >10 x ULN	CTCAE grades 1-4
Hematology		
Hemoglobin	Hgb decreased (anemia) <LLN - ≥ 100 g/L <100 - ≥ 80 g/L < 80 g/L	CTCAE grade 1-3
	Hgb increased >ULN - ≤ 20 g/L above ULN >20 g/L above ULN - ≤ 40 g/L above ULN >40 g/L above ULN	CTCAE grade 1-3

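### The SAP plans no summary of CGM time below 70 mg/dL, no serum glucose threshold and no hypoglycaemia grouping, and it drops CGM readings below 39 mg/dL

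*SAP*

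**What the plan says.** **CGM.** SAP 8.3.3.2 lists "Change from baseline in percent of time spent in target blood glucose range of" 70 to <140 mg/dL, then time at 140 to <200 and at 200 mg/dL or above. No band lies below 70. SAP 8.3.3.1 treats readings below 39 or above 401 mg/dL as missing and accepts a day with at least 202 of 288 readings. CGM is done only in subjects with CFRD, about 30 of 60. The endpoint list in SAP 5.1.3 is open-ended, and SAP 8.5 sends further CGM parameters and insulin dose to a separate document.

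**Laboratory.** Glucose is in the serum chemistry panel (Protocol Table 11-1). SAP 8.4.2 summarises chemistry by visit and lists individual values. Its threshold analysis, however, counts subjects "meeting the threshold analysis criterion at least once during the TE period will be summarized for select LFT parameters". The non-LFT chemistry rows of SAP Table 12-3 are albumin, amylase, creatinine, lipase, total protein and creatine kinase. There is no glucose row there, nor in the labelling table at the end of Appendix F.

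**Adverse events.** SAP 8.4.1.1 begins "For this study, elevated transaminase events and rash events, as determined by MedDRA preferred terms" and names no other special-interest category. SAP 8.4.1 tabulates all treatment-emergent events by system organ class and preferred term.

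**Population.** The Protocol Synopsis says that "approximately 50% may be enrolled while using insulin", at no more than 0.3 units/kg/day. Safety and tolerability form the secondary objective.

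**The concern.** The trial is designed to detect a fall in post-load glucose in subjects of whom about half may be injecting insulin, so low glucose is a natural thing for the safety objective to look at. The data are collected, by CGM in the CFRD subjects and by serum chemistry in everyone, but no planned table shows how many subjects spent time below 70 mg/dL, or whether they were insulin users. The rule on readings below 39 mg/dL adds to this. A reading set to missing leaves the denominator of every percent-of-time measure, so very low values can change the reported time in target without appearing anywhere as low.

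**Working it through.** **1. The plan's own figure.** SAP 6.2 claims "more than 95% power to detect a mean decrease from baseline of -30 mg/dL" with SD 45 mg/dL, 60 subjects and 10% dropout. Evaluable n = 60 × 0.9 = 54, and the noncentrality is (30/45) × √54 = 4.90. The exact 2-sided one-sample t-test at 0.05 then has power 99.8% (99.9% with n = 60). The claim is reproduced, and nothing below alters it.

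**2. What the three bands reveal.** On valid readings, the three planned bands plus time at 39 to <70 sum to 100%. Hence:

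mean change in time at 39 to <70 = −(sum of the three mean band changes).

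The mean can be recovered by subtraction. The SD and the number of subjects affected cannot.

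The documents give no CGM distribution. Assume a baseline of 2 / 50 / 30 / 18% for <70, 70 to <140, 140 to <200 and ≥200, and move 5 points to 39 to <70:

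| Time comes from | Time in target | 140 to <200 | ≥200 | How the planned tables read |
|---|---|---|---|---|
| 70 to <140 | −5 | 0 | 0 | worse |
| 140 to <200 | 0 | −5 | 0 | better |
| ≥200 | 0 | 0 | −5 | better |

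The direction of the reported change depends on where the time came from.

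**3. Effect of the below-39 rule.** A day stays valid with 288 − 202 = 86 readings missing, which is 86 × 5 / 60 = 7.2 hours. Assume a day of 144 readings in target, 86 at 140 to <200, 52 at ≥200 and 6 at 39 to <70 (total 288), so time in target is 144/288 = 50.0%. Now let some readings fall below 39 and be dropped:

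| Readings moved below 39 | From | Time in target under the SAP rule | Time in target with all 288 kept |
|---|---|---|---|
| 12 (1 h) | 140 to <200 | 144/276 = 52.2% | 144/288 = 50.0% |
| 36 (3 h) | 140 to <200 | 144/252 = 57.1% | 144/288 = 50.0% |
| 12 (1 h) | target | 132/276 = 47.8% | 132/288 = 45.8% |
| 36 (3 h) | target | 108/252 = 42.9% | 108/288 = 37.5% |

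In the first row, subtraction gives 6/276 = 2.2% at 39 to <70, against 6/288 = 2.1% before the shift, so the hour below 39 is not visible. If those readings were kept and counted as below 70, the figure would be (6 + 12)/288 = 6.3%.

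**4. What each planned output can show about low glucose.**

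| Output | What it shows | What it does not show |
|---|---|---|
| CGM bands | mean time at 39 to <70, by subtraction | subjects affected; any reading below 39; insulin users with IGT |
| Serum glucose by visit | mean, SD, median, minimum; individual listing | count of subjects below a threshold |
| Adverse event tables | hypoglycaemia that was reported, by preferred term | related terms taken together; split by insulin use |

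**The case against.** The strongest reply is that the plan is not blind to low glucose. Reported hypoglycaemia appears in the preferred-term tables, with further tables by severity, seriousness and relationship. Serum glucose is summarised at each visit with its minimum and is listed by subject. Mean CGM time at 39 to <70 follows by subtraction. All of this stands.

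A reader might infer that any move into hypoglycaemia would look like benefit. The documents do not support that. Time that leaves the target range for 39 to <70 lowers the target-range endpoint, and where time in the high bands falls without a matching rise in target, the tables show the mismatch. A reader might also infer that the safety outputs stop at 70 mg/dL. They do not; they use no glucose threshold at all.

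Nor can it be said that CGM lows would go unreported. Protocol 10.7 says that subjects and their parents or guardians "should not be informed of their study-related CGM, SwCl, spirometry, FE-1, and blood biomarker results", but it does not withhold CGM from investigators. The list of assessments reviewed for adverse events in Protocol 13.1.1.2 is not exhaustive, so the absence of CGM from it proves little.

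Glucose is not singled out in the threshold text either. SAP 8.4.2 limits that summary to liver parameters, so on its wording none of the non-LFT rows is used. Finally, time below 70 may be specified in the separate document to which SAP 8.5 refers.

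What survives is the lack, in this SAP, of any subject-level summary of low glucose, together with the unhandled effect of the below-39 rule.

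**Conclusion.** The point holds as a gap in descriptive safety reporting. This SAP specifies no time-below-70 summary, no glucose threshold and no hypoglycaemia grouping, and it sets readings below 39 mg/dL to missing. Shifts into low glucose from the bands at 140 mg/dL or above would not register as harm. Where readings fall below 39 and leave the denominator, time in target can rise: by 2.2 percentage points for 1 hour and 7.1 for 3 hours on the assumed day, if the time came from 140 to <200. If it came from the target range, time in target still falls, but by less than it should.

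These figures illustrate a mechanism and do not estimate its frequency. They rest on assumed distributions. They also require the device to report values below 39; if its lowest reported value is 39 or more, the rule removes no low readings and only the missing summary remains. The documents do not say which applies. The conclusion covers this SAP and does not show that the trial as a whole lacks such a measure. The primary test and its power are unaffected.

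**What to change.** All of this uses data already collected.

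1. Add to SAP 8.3.3.2 the percent of CGM time below 70 mg/dL and the number of subjects with any such time, by insulin use at baseline (already a planned variable in SAP 8.2.2). If the separate document already specifies this, cross-reference it. Amend SAP 8.3.3.1 so that device-reported readings below 39 mg/dL count as time below 70 and stay in the denominator, or at least report their number at each visit. Without that amendment the new table would omit the lowest readings.
2. Optionally, add a low serum glucose row to Table 12-3 at the plan's own bound of 70 mg/dL (3.89 mmol/L), and widen the threshold text in SAP 8.4.2 beyond liver parameters so that the row is used.
3. Optionally, group the hypoglycaemia preferred terms and show them by baseline insulin use. This and item 2 also reach insulin users with IGT, who have no CGM.

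The cost is SAP wording and a few more descriptive tables. No assessment is added, and sample size, alpha, power and the primary analysis do not change.

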## 8.4 Safety Analysis

All safety analyses will be based on data from the TE period based in the Safety Set, unless otherwise specified.

The overall safety profile of study drug will be assessed in terms of the following safety and tolerability endpoints:

- Treatment-emergent adverse events (TEAEs)
- Clinical laboratory values
- ECGs
- Vital signs
- Pulse oximetry

Only descriptive analysis of safety will be performed, and no statistical testing will be performed.

### 8.4.1 Adverse Events

For analysis purposes, AEs will be classified as pretreatment AEs, TEAEs, and post-treatment AEs, defined as follows:

**Pretreatment AE:** any AE that occurred before the first dose date of study drug

**TEAE:** any AE that worsened (either in severity or seriousness) or that was newly developed at or after the first dose date of study drug through the end of the TE period

**Post-treatment AE:** any AE that worsened (either in severity or seriousness) or that was newly developed after the TE period

For AEs with completely missing or partially missing start dates, if there is no clear evidence that the AEs are pre-treatment or TEAE, the AEs will be classified as TEAEs.

Details for imputing missing or partial start dates of adverse events are described in [Appendix D](#).

An overview of all TEAEs will be summarized in the following categories:

- Number of TEAEs
- Subjects with any TEAEs
- Subjects with TEAEs by strongest relationship
- Subjects with TEAEs by maximum severity

- Subjects with TEAEs leading to study drug discontinuation
- Subjects with TEAEs leading to study drug interruption
- Subjects with Grade 3/4/5 TEAEs
- Subjects with related TEAEs
- Subjects with serious TEAEs
- Subjects with related serious TEAEs
- Subjects with TEAEs leading to death

The following summary tables of TEAEs will be presented by MedDRA System Organ Class (SOC) and Preferred Term (PT) using frequency counts and percentages (i.e., number and percentage of subjects with an event):

- All TEAEs
- Grade 3/4/5 TEAEs
- TEAEs by strongest relationship
- TEAEs by maximum severity
- TEAEs leading to treatment discontinuation
- TEAEs leading to treatment interruption
- Related TEAEs
- Serious TEAEs
- Related serious TEAEs
- TEAEs leading to death

When summarizing the number and percentages of subjects, subjects with multiple occurrences of the same adverse event or a continuing adverse event will be counted once, and only the maximum severity level will be presented in the severity summaries, and the strongest relationship level in the relationship summaries.

All AEs, including pretreatment AEs, TEAEs, and post-treatment AEs, will be presented in an individual subject data listing based on the All Subjects Set. In addition, separate listings containing individual subject adverse event data for TEAEs leading to treatment discontinuation, TEAEs leading to treatment interruption, Grade 3/4/5 TEAEs, SAEs, and all deaths will be provided. Listings for SAEs and deaths will include a flag indicating the TEAE status.

#### **8.4.1.1 Adverse Events of Special Interest**

For this study, elevated transaminase events and rash events, as determined by MedDRA preferred terms in [Appendix E](#), are considered as adverse events of special interest.

For treatment-emergent elevated transaminase events and rash events, the following categories will be summarized by treatment group:

- Subjects with events

- Subjects with events by maximum severity
- Subjects with events leading to treatment discontinuation
- Subjects with events leading to treatment interruption
- Subjects with serious events
- Subjects with related serious events
- Subjects with events leading to death
- Duration of events
- Time-to-onset of first event

In addition, for treatment-emergent rash events, these categories will be summarized for the following subgroups:

- Sex (male, female)
- Female subjects with concomitant hormonal therapy (Yes, No)

